Aim 2: This aim will test between group differences in number of cigarettes smoked over time among micro-randomized trial (N=80) and EMA-only control group participants (N=80). Sample size calculations were based on findings from a recent app-based mindfulness meditation trial for smoking reduction. This trial only delivered intervention content for 14 days (as opposed to the 30 days proposed here) and found a significant reduction in 3.8 cigarettes/day in the intervention group compared to an increase in 0.8 cigarettes/day in the control group, which translates to an effect size of $d=0.651$ ($f=0.326$). Power estimation for between group repeated measures ANOVA and interactions were conducted with G-Power. Assuming an alpha level of 0.05, a sample size of N=160 will allow us to detect effects in reduction of cigarettes per day of $f=0.326$ and larger with a power of 0.80. Multiple imputation will be used for missing data and the full sample will be analyzed.

IV. Participants:

Describe the study participants and the population from which they will be drawn. Specify the inclusion and exclusion criteria. If you plan to include children, note their ages and whether you will include children in foster care. Note if the participants are particularly vulnerable in terms of cognitive limitations, education, legal migration status, incarceration, poverty, or some combination of factors.

A. Inclusion Criteria:

Participants will be young adult men and women who: 1) live in the U.S.; 2) read English; 3) are between 18 and 30 years of age; 4) own a smartphone with iOS and Android operating system and GPS capabilities; 5) are carrying their smartphone with them every day; 6) are willing to participate in the study for 44 days and give the research team access to the phone GPS data; 7) have smoked ≥ 100 cigarettes in their lives and currently smoke at least 1 cigarette per day on 3 or more days of the week (full trial: smoke at least 3 cigarettes per day on 5 or more days of the week); 8) are planning to quit smoking within the next 30 days.

B. Exclusion Criteria:

There are no additional exclusion criteria for participants that meet inclusion criteria.

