After informed consent has been obtained, participants will be asked for the contact information (email address and phone number) so that the study team can stay in contact. Final enrollment of a participant will depend on identity verification. Since data collection for this study will take place remotely, participants will be required to submit a picture of an official ID document for verification of their identity and age, a procedure that [name] has found to be feasible in his previous studies. After verification of identity, participants will be enrolled into the study. Only the participant picture on the ID (headshot) will be retained for biochemical verification of smoking abstinence. The ID document will subsequently be deleted after validation of participant details for enrollment.

Baseline survey: Initially, all participants will complete a baseline survey on the online survey platform Qualtrics, to assess basic demographics, smoking and other tobacco use behavior, including e-cigarettes, nicotine dependence, quitting history and current quit motivation, frequency and intensity of smoking urges, and other substance use behavior including alcohol, cannabis, and other illicit drugs. Smoking-specific experiential avoidance, a measure to assess a person's willingness to experience negative mental states (e.g., urges, mood, thoughts), will be assessed with the Avoidance and Inflexibility Scale. Trait mindfulness will be assessed with the FIT-60 (Flexibility Index Test).¹⁴³ Baseline measures will also include trait negative affect and psychological distress.

EMA data collection: Before EMA data collections, participants will be contacted on the phone to receive detailed instructions on how to use the EMA study app. Participants will use their own smartphones and the study app to collect data on smoking situations over the course of 14 days (EMAs of smoking situations and smartphone location sensor data). Participants will complete 3 randomly prompted EMA surveys per day and will report every time they smoke a cigarette. A random subset of these cigarette reports will trigger up to 3 EMA smoking survey prompts per day.

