Analyses for message acceptability testing will utilize a mixed methods approach. For the quantitative analyses, the **primary outcome** will be message acceptability expressed as the average score of Likert responses to helpfulness to cope with smoking urges or craving and to support quit attempts and acceptability of message content and design. Messages will be ranked by score and messages with low scores will be either modified in line with qualitative participant feedback or removed before moving to the next study phase. Analyses assessing message acceptability across age, gender, and race/ethnicity will include independent variables age, gender, race/ethnicity, educational attainment, psychological flexibility, smoking frequency, quit motivation, and past quitting attempts. These quantitative analyses on message acceptability will be supplemented with qualitative analyses involving inductive and deductive coding of participants' open-ended responses to inform how messages should be modified.

Analytical strategy Aim 1: To compare CBT and ACT intervention message efficacy.

Aim 1 analyses to test the hypothesis of a proximal benefit of urge reduction messages will be conducted using a centered and weighted least squares method, which estimates treatment effects and allows inclusion of covariates. The method is similar to GEE and multi-level models in that it accounts for dependence of responses within individuals due to repeated measures via the use of robust standard errors. Moreover, the method takes advantage of the sequential randomization to estimate causal treatment effects. The **primary outcome** will be participants' rating of **smoking urge** in EMA-post surveys, prompted 15 minutes after intervention message delivery, and controlling for the ratings in EMA-pre surveys. The main independent variable will be message type: **CBT versus Mindfulness/ACT versus a Control Message** ("Thank you for completing the survey"). We will also **test differences in efficacy between CBT versus Mindfulness/ACT**. We will use **multiple imputation** to impute missing data in EMA-post surveys.

Analytical strategy Aim 2: To test if urge reduction messages change smoking behavior over time.

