Aim 2 analyses will use data from both the micro-randomized trial group (N=80) and the EMA control group (N=80). **Primary outcome:** The primary outcome will be self-reported number of cigarettes/day in the past week at 45-day, 3-, and 6-month follow-up. GEE will examine cigarettes/day at each follow up by group (micro-randomized trial vs. EMA-only control). Independent variables are group membership, variables that differ by group at baseline, gender, and nicotine dependence. Again, **multiple imputation procedures** will be used to impute missing data at follow-up.

Analytical strategy Aim 3: Explore moderation effects of substance co-use (cannabis, alcohol, other drugs) and exposure to specific location (home, work, bars) on urge reduction message efficacy.

Based on our data on high co-use of cigarettes with cannabis and alcohol, as well as changes in perceived reward of smoking cigarettes when under the influence of cannabis or alcohol, analyses in this aim will explore if message efficacy is moderated by substance co-use (whether a participant currently is under the influence of another substance, e.g., cannabis, alcohol, other drugs). Centered and weighted least squares

models¹⁵² similar to those for Aim 1 will be estimated with predictors intervention message type (CBT, Mindfulness/ACT, control), substance use (cannabis, alcohol, other drugs, none), and their interaction. Based on existing evidence on alcohol and cannabis co-use as barrier to cigarette smoking cessation, we hypothesize that intervention message efficacy will be reduced when participants are under the influence of another substance. However, analyses for this aim will enable us to explore if specific types of messages (CBT, Mindfulness/ACT, and subconstructs) are more helpful in co-use situations.

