Moreover, we will explore aspects of intervention message-situation fit. We will test if specific locations (e.g., home, work, bars) impact intervention message efficacy. Mixed models will be estimated containing the predictors intervention type (CBT, Mindfulness/ACT, control), location (home, work, bar, other locations), and their interaction. We will explore other situational characteristics and intervention message-situation fit based on affect, arousal, stress, and the presence of other smokers. We do not have specific hypotheses about moderation effects of location and other situational characteristics, but findings will inform future interventions using adaptive messages over time to improve intervention-message situation fit and intervention efficacy.

5. Answer the following if they are relevant to your study design:

- A. If the study has different arms, explain the process for assigning participants (intervention/control, case/control), including the sequence and timing of the assignment.

We will use stratified block randomization to assign participants into the micro-randomized trial intervention group (N=80) and EMA-only control group (N=80). The stratification variable known to robustly impact smoking cessation success will be level of nicotine dependence (smoking within first 30 mins after waking, y/n).¹³¹ Gender will be used as additional stratification variable. We will generate a randomization table and participants will be assigned after baseline completion.

- B. If human biospecimens (blood, urine, saliva, etc.) will be collected, provide details about who will collect the specimen, the volume (ml) and frequency of collection, how the specimen will be used, stored, identified, and disposed of when the study is over. If specimens will be collected for use in future research (beyond this study), complete the “Biospecimen Repository” section below.

N/A

- C. If genetic/genomic analyses are planned, address whether the data will be contributed to a GWAS or other large dataset. Address returning unanticipated incidental genetic findings to study participants.

N/A

- D. If clinical or laboratory work will be performed at JHU/JHH, provide the JH Biosafety Registration Number.

N/A

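### The Aim 2 primary model admits baseline cigarettes/day only through an undefined imbalance rule, which costs precision and saves nothing

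*Combined protocol and SAP*

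**What the plan says.** Section V.C.4 (Aim 2) takes as primary outcome the self-reported past-week cigarettes/day at 45 days, 3 months and 6 months, and states that "GEE will examine cigarettes/day at each follow up by group". The covariate sentence reads: "Independent variables are group membership, variables that differ by group at baseline, gender, and nicotine dependence". Baseline is neither one of the outcome time points nor a named covariate. Nothing else in the document defines what counts as differing at baseline.

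Four other places bear on this:

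- **V.C.4, Aim 1.** The pre-message value is fixed in the model: the urge outcome is analysed after the message "and controlling for the ratings in EMA-pre surveys".
- **III.B, Aim 2.** The sample size is framed as change from baseline. N=160 "will allow us to detect effects in reduction of cigarettes per day", using a repeated measures ANOVA.
- **V.C.1, Baseline survey.** Everyone reports "basic demographics, smoking and other tobacco use behavior, including e-cigarettes, nicotine dependence" and further items. Cigarettes/day is not mentioned by name.
- **V.C.5.A.** The stratification factors are smoking within 30 minutes of waking (yes/no) and gender, not cigarettes/day. On timing: "We will generate a randomization table and participants will be assigned after baseline completion".

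**The concern.** How much a person smoked at entry is likely to be among the best predictors of how much that person smokes at follow-up. Eligibility for the full trial (IV.A) sets a floor of 3 cigarettes per day on 5 or more days a week and no ceiling, so entry values can vary widely. Leaving this variable to a look at the observed imbalance has two consequences.

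First, the primary model is settled after data are seen, by a rule that different analysts could apply differently. V.C.5.F states that staff are not blind to assignment.

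Second, in a randomised trial a baseline covariate earns its place by predicting the outcome, not by happening to be imbalanced. An imbalance rule will usually leave the covariate out, and the precision it would have given is lost.

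A related, secondary point: three follow-ups share primary status, and the covariate list has no time or group-by-time term. It is unclear whether the primary contrast is one overall group effect or a separate test at each follow-up.

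**Working it through.** **1. The plan's own figure.** Inputs from III.B: "Assuming an alpha level of 0.05, a sample size of N=160", d=0.651 (f=0.326), "and larger with a power of 0.80". Two-sided testing is assumed.

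- f = d/2 = 0.3255, which agrees.
- At one follow-up with 80 per arm, the noncentrality is 0.651 × √(80/2) = 4.12, giving power 0.984.
- 80% power at d=0.651 needs only 38 per arm. At 80 per arm, 80% power corresponds to d=0.446.
- Repeated measures forms with 2 to 4 measurements and correlations from 0 to 0.99 also give about 0.98 or more.

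The stated 0.80 is therefore true only as a lower bound, and the planned effect carries slack.

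**2. How often the rule admits baseline.** Assumptions: imbalance means a t-test p<0.05, and baseline cigarettes/day correlates 0.3 with the dependence item. Stratification balances dependence, so the variance of the between-arm baseline difference shrinks by 1 − 0.3² = 0.91. The chance of admission is P(|Z| > 1.96/√0.91) = P(|Z| > 2.05), about 0.04. In about 96% of trials baseline stays out.

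**3. Precision.** Let r be the baseline-to-follow-up correlation, which the documents do not give. Suppose dependence predicts follow-up only through baseline. The residual variance is then 1 − (0.3r)² with dependence alone and 1 − r² with baseline added. The variance ratio, always against never adjusted, is (1 − r²)/(1 − 0.09r²).

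| r | variance ratio | interval-width ratio | narrower by |
|---|---|---|---|
| 0.3 | 0.910/0.992 = 0.917 | 0.958 | about 4% |
| 0.5 | 0.750/0.978 = 0.767 | 0.876 | about 12% |
| 0.7 | 0.510/0.956 = 0.534 | 0.730 | about 27% |

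**4. Power and type I error.** Simulation: 80 per arm, one follow-up, normal outcome, gender and dependence balanced and in the model. It used 60,000 trials under the null and 20,000 per alternative. Each cell gives the values for r = 0.3 / 0.5 / 0.7.

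| true effect | plan's rule | baseline always in |
|---|---|---|
| d=0.30 | 0.47 / 0.49 / 0.49 | 0.50 / 0.59 / 0.74 |
| d=0.446 | 0.81 / 0.82 / 0.83 | 0.84 / 0.90 / 0.97 |
| d=0.651 | 0.984 / 0.987 / 0.992 | 0.989 / 0.997 / >0.999 |

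Type I error under the rule is 0.047 / 0.045 / 0.040, which is nominal to mildly conservative.

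Hand check of one cell, always adjusted, d=0.30, r=0.5: SE = √(2/80) × √0.75 = 0.137. Then 0.30/0.137 − 1.96 = 0.23, giving power of about 0.59.

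**5. Sensitivity to the undefined threshold.**

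| threshold | type I error | power at d=0.446 |
|---|---|---|
| p<0.10 | 0.047 / 0.043 / 0.034 | 0.81 / 0.82 / 0.85 |
| p<0.20 | 0.045 / 0.039 / 0.029 | 0.82 / 0.83 / 0.87 |

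Fixed adjustment is better in every case.

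**6. Averaging three follow-ups.** With assumed between-follow-up correlations of 0.6 / 0.6 / 0.7, power at d=0.30 is 0.60 / 0.62 / 0.60 under the rule and 0.65 / 0.77 / 0.92 with baseline always in.

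**7. Secondary point.** If success at any one of three follow-ups counted, each tested at 0.05, the family-wise error would be 0.126, 0.118, 0.109 and 0.098 for between-follow-up correlations of 0.5, 0.6, 0.7 and 0.8. The plan does not state that success rule, so the figure is conditional.

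**The case against.** The strongest reply is that the planned analysis is valid: no bias, no inflated type I error, and no material power loss at the effect the trial was planned for. That stands. What remains is interval width and power at effects smaller than planned. Smaller effects are plausible on the document's own account, since V.C.5.F says that self-monitoring in the control group may itself reduce smoking.

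The size also rests on assumptions. At r=0.3 the gain is slight, and 27% needs r=0.7. Participants plan to quit and follow-up runs to 6 months, so r could be modest and could decline over time. Nicotine dependence is already in the model and may recover more than assumed. If its correlation with baseline were 0.6, the ratio (1 − r²)/(1 − 0.36r²) would cut the gains to about 3% / 9% / 21%. The direction does not change.

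The simulation uses one complete, normally distributed follow-up. The plan uses GEE over three follow-ups with multiple imputation, and quitters will contribute zeros. Open selection among several baseline variables was not simulated. The figures are therefore indicative.

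Finally, the source is a brief analysis section in an IRB form, and III.B mentions interactions, so a time interaction may have been contemplated. Brevity explains the gap but does not supply the rule or the model terms. The N=10 pilot is unaffected, because it has no 3- or 6-month surveys.

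**Conclusion.** The concern holds, as a matter of efficiency and pre-specification rather than validity. That the covariate list omits baseline cigarettes/day and leaves the imbalance rule undefined is plain from the text. Under the p<0.05 reading the rule acts almost like no adjustment. The loss is a confidence interval that could be about 4% to 27% narrower for r between 0.3 and 0.7, with a dependence-baseline correlation of 0.3. At a true effect of 0.30 SD, that means 3 to 25 percentage points of power at a single follow-up. At d=0.651 the loss is immaterial. The unclear primary contrast is a real but secondary ambiguity, and the conclusion does not depend on it.

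**What to change.** Replace the Aim 2 covariate sentence with a closed list: group, follow-up time, group-by-time, baseline cigarettes/day from the pre-randomisation survey, gender, and smoking within 30 minutes of waking. Delete the clause on variables that differ at baseline. Use the same variables in the imputation model.

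Name one primary contrast, for example the group effect averaged over the three follow-ups, and make the time-specific contrasts secondary.

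Confirm that the baseline survey carries the same past-week cigarettes/day item as the follow-up surveys. V.C.1 describes its content only in general terms. Do not take the baseline value from the 14-day diaries. Both arms follow the same procedures in that phase, but it appears to come after assignment: follow-up is counted from randomisation, end of treatment is day 45, and 14 + 30 = 44 days of data collection precede it.

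The cost is a change of wording and one degree of freedom for the baseline covariate. No visit or participant is added, provided the baseline item exists.

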Aim 1: A sample size of 80 participants receiving 3 randomized messages per day for 30 days will provide 7,200 observations. Across person-days, there will be an average of one prompt per day for each of the 3 conditions CBT, Mindfulness/ACT, and control (balance across person-days). Power estimations were conducted using an online tool specifically developed for sample size calculations for micro-randomized trials by consultant [name]. Assuming a message randomization probability of 1/3 (33% CBT, 33% Mindfulness/ACT, 33% control), a quadratic effect over time (initially smaller as participants are getting used to the intervention, increasing over time to peak at day 20, and decreasing thereafter as participants may get desensitized), and an average compliance rate of 75%, linearly decreasing over time, a sample size of N=80 participants will allow for detecting a standardized mean difference between CBT, Mindfulness/ACT, and control conditions on the primary outcome self-reported smoking urge of $d=0.1$ with a power of 0.8 and an alpha level of 0.05. This measure of effect size is a generalization of Cohen's d (standardized mean difference), with the difference that the standardization is by the average standard error over the entire study, with multiple treatments for each person. A Cohen's d of 0.1 is considered a small effect. A previous EMA study found that playing Tetris (analogous to a CBT distraction technique) decreased substance use urges with a mean effect size of $f^2=0.12$ (medium sized effect). Given these effect sizes in the existing literature, we will be adequately powered to detect effects in Aim 1 analyses.

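### Location moderation in Aim 3 uses mixed models with no stated random effects or variance estimator, while Aim 1 and co-use moderation use weighted least squares with robust standard errors

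*Combined protocol and SAP*

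**What the plan says.** All three analyses are described in section V.C.4.

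- **Aim 1.** The proximal effect on urge is "conducted using a centered and weighted least squares method, which estimates treatment effects and allows inclusion of covariates". Two reasons are given for this choice: "it accounts for dependence of responses within individuals due to repeated measures via the use of robust standard errors", and "the method takes advantage of the sequential randomization to estimate causal treatment effects".
- **Aim 3, substance co-use.** The same class of model is kept, "similar to those for Aim 1 will be estimated with predictors intervention message type (CBT, Mindfulness/ACT, control), substance use (cannabis, alcohol, other drugs, none", with the interaction.
- **Aim 3, location.** The method changes: "Mixed models will be estimated containing the predictors intervention type (CBT, Mindfulness/ACT, control), location (home, work, bar, other locations), and their interaction". The text gives no reason. It does not mention random effects, the type of standard error, centring of message type or adjustment for the pre-message urge rating.
- **Other situational characteristics** (affect, arousal, stress, other smokers present) are to be explored too, with no model named.

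The plan is open about the status of this work: "We do not have specific hypotheses about moderation effects of location and other situational characteristics".

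**The concern.** Location and co-use are moderators of the same kind. Both vary over time within a person, and both are crossed with the same randomized messages in the same participants. The two arguments for WCLS therefore hold for location as much as for co-use.

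The wording for location permits a random-intercept model with model-based standard errors. Such a model assumes that everyone responds equally to a given message type. If they do not, person-to-person variation in the message effect is missing from the standard error of the interaction. The loss grows as location mix differs more between people. That is likely here, because the geofences are built around each participant's own high-risk places (section V.C.1, purpose of the EMA training phase).

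The plan intends the findings to guide later adaptive messaging. A location that only appears to moderate the effect could therefore shape the next intervention.

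**Working it through.** **Inputs from the plan (section III.B, Aim 1).** "A sample size of 80 participants receiving 3 randomized messages per day for 30 days will provide 7,200 observations": 80 × 3 × 30 = 7,200, which reproduces. "Assuming a message randomization probability of 1/3 (33% CBT, 33% Mindfulness/ACT, 33% control". Average compliance is 75%, so 7,200 × 0.75 = 5,400 answered prompts, or 90 × 0.75 = 67.5 per person. The target effect is d = 0.1. The Aim 1 power of 0.80 recomputes as 0.81 to 0.87, depending on the unstated initial effect and compliance slope, and is not at issue. The plan states no error rate for the location analysis.

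**Inputs that must be assumed.** These are the between-person SD of the message effect (τ, in residual SDs), the location shares, and how far location mix differs between people.

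**Closed form for one coefficient.** Take one active message against control. Each person contributes m = 67.5 × 2/3 = 45 answered prompts, and p = 1/2 among them. Treat location as one indicator with between-person intraclass correlation ICC. If the random message slope is omitted, the true variance of the interaction exceeds the model-based variance by about

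f = 1 + m·p(1−p)·ICC·τ² = 1 + 11.25·ICC·τ²

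and a nominal 5% test rejects at 2Φ(−1.96/√f).

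- ICC 0.17, τ = 0.2: f = 1.075, rejection 5.9%. With τ = 0.3: f = 1.169, 7.0%.
- ICC 0.50, τ = 0.2: f = 1.225, 7.7%. With τ = 0.3: f = 1.506, 11.0%.
- ICC 0 or τ = 0: f = 1, 5%.

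**Simulation of the layout as planned.** Three messages, four locations, a joint test on (3−1)(4−1) = 6 df, and no true average interaction. Assumed location shares are 50/25/10/15%. Person-level mixes come from a Dirichlet distribution with concentration 5 (moderate differences, ICC = 1/(1+5) = 0.17), 1 (mostly one type, ICC 0.50) or infinite (same mix for all). Each scenario had 400 to 1,000 runs. The Monte Carlo error at 5% with 400 runs is √(0.05 × 0.95/400) = 1.1 points. Two values show two sets of runs. Dashes were not run.

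| Person-level SD | Location-specific SD | Location mix | Random intercept: joint | Random intercept: single | WCLS: joint | Random slopes: joint |
|---|---|---|---|---|---|---|
| 0 | 0 | moderate | 4.2–5.6% | 4.4–4.9% | 4.0% | 3.0% |
| 0.1 | 0 | moderate | 6.1% | 5.3% | – | – |
| 0.2 | 0 | moderate | 6.2–8.8% | 5.4–6.2% | 4.2% | 3.0% |
| 0.3 | 0 | moderate | 11.9–13.2% | 7.3–7.4% | 5.5% | 3.8% |
| 0 | 0.2 | moderate | 11.1% | 7.3% | – | – |
| 0 | 0.3 | moderate | 17.5–19.4% | 8.2–8.7% | 3.5% | 3.5% |
| 0.2 | 0.2 | moderate | 15.4% | 7.5% | – | – |
| 0.3 | 0.3 | moderate | 23.0–26.0% | 10.3–10.4% | 5.2% | 3.5% |
| 0.2 | 0 | mostly one type | 14.6% | 6.8% | – | – |
| 0.3 | 0 | mostly one type | 25.9% | 10.2% | – | – |
| 0.3 | 0 | same for all | 4.9% | 4.5% | – | – |
| 0 | 0.3 | same for all | 12.1% | 7.4% | – | – |

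The single-coefficient column agrees with the closed form. Serial correlation alone (AR(1), 0.5) left the joint test at 5.0%, because messages are re-randomized at every prompt. The driver is variation in message effects, not repeated measurement as such.

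**The case against.** A reader might infer that the move to mixed models itself puts these tests at 10% to 19% in place of 5%. The documents do not support that, for four reasons.

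- The plan lists predictors and is silent on random effects. That silence does not establish a random-intercept-only model, and a mixed model with matching random slopes held at 3.0% to 3.8%. The Aim 1 text itself groups WCLS with multilevel models as ways of handling within-person dependence.
- Such a range needs τ of about 0.2 to 0.3, two to three times the d = 0.1 that Aim 1 is powered for. The documents give no value. At τ = 0.1 the joint rate was 6.1%, and with no heterogeneity there is no inflation.
- It depends on the test. A simulation of one pooled contrast, active message by location, gave 9.9% to 18.8% at these SDs. The closed form for that contrast (67.5 × 2/9 = 15 in place of 11.25) gives about 7% (ICC 0.29, SD 0.2) to 13% (ICC 0.50, SD 0.3). Single coefficients in the planned layout reached only about 10%.
- The 5% level is borrowed from Aim 1. The location analysis is exploratory and has no stated alpha.

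Nor does it follow that co-use and location results could not be compared. Both models estimate a message-by-moderator interaction, and both estimators were unbiased under the null. It is also fair to say that the form asks only for a brief analysis plan.

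All of this limits the size of the point. It does not explain why one moderator gets a method the plan has justified and the other gets an unspecified one.

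**Conclusion.** The point holds in conditional form. The change of method within Aim 3 is real and unexplained, and the location model is under-specified. Its standard errors are too small if three things hold together: a random intercept only, model-based standard errors, and message effects that vary between people. Variation in the person-level effect also needs location mix to differ between people. Location-specific variation does harm even when the mix is shared (12.1% at SD 0.3).

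Over assumed SDs of 0 to 0.3, the joint test's false-positive rate runs from about 5% to about 26%. The upper end arises when people stay mostly in one location type, or when both kinds of variation are at 0.3. Single coefficients run from about 4% to 10%. WCLS gave 3.5% to 5.5% in the five scenarios where it was run. None of these rates follows from the plan's own figures. No confirmatory claim rests on the analysis, so severity is low to moderate.

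**What to change.** In section V.C.4, Aim 3, replace the mixed models for location with the same WCLS and robust standard errors used for Aim 1 and co-use. Take location at the pre-message survey as the moderator. Name the same model for affect, arousal, stress and presence of other smokers.

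If the team prefers a mixed model, it should state random message and message-by-location slopes and name the variance estimator. That also controls the error.

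The cost is wording, since WCLS is already planned for two analyses. When message effects do not vary, the WCLS standard error is slightly larger: 0.047 against 0.045 in the simulation of the pooled contrast, a ratio of 1.04.
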